## 1.0 TRIAL SUMMARY

Short Title:	A Phase 2 Study of V920 Ebola Virus Vaccine Candidate in HIV Infected Adults and Adolescents
Manufacturer Product Identifier	V920
Trial Phase	Phase 2
Clinical Indication	Prevention of Ebola Disease
Trial Type	Randomized, multi-center
Type of control	Placebo
Route of administration	IM
Trial Blinding	Double blind
Select Cohorts	HIV-infected individuals within each of the five cohorts will be randomly assigned to receive V920 or placebo: Cohort 1: 50 adults with CD4 $\geq$ 500 cells/mm $^3$ Cohort 2: 50 adults CD4 > 350 and < 500 cells/mm $^3$ Cohort 3: 50 adults CD4 $\geq$ 200 and $\leq$ 350 cells/mm $^3$ Cohort 4: 50 adolescents CD4 $\geq$ 200 cells/mm $^3$ Cohort 5: 50 adults and adolescents CD4 $\geq$ 200 cells/mm $^3$
Number of trial subjects	Approximately 250 subjects will be enrolled.
Estimated duration of trial	The Sponsor estimates that the trial will require approximately 30 months from the time the first subject signs the informed consent until the last subject's last study-related phone call or visit.
Duration of Participation	Each subject will participate in the trial for approximately 13 months, from the time the subject signs the Informed Consent Form (ICF) through the final contact. After a screening phase of up to one month, each subject in Cohorts 1 to 4 will be receiving one dose of assigned vaccine/placebo and each subject in Cohort 5 will be receiving one dose of assigned vaccine/placebo at Day 0, and followed by a second dose of the same vaccine/placebo treatment at Day 56. Each subject will be followed for 365 days from the first vaccination.
Randomization Ratio	200:50 (4:1)

A list of abbreviations used in this document can be found in Section 12.0.

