#### 3.2 Secondary Objective(s)

- (1) **Objective:** Evaluate VSV viremia and shedding after administration of V920.
- (2) **Objective:** Evaluate ZEBOV-specific antibody responses induced by V920 through D180 and D365.
- (3) **Objective:** Evaluate the impact of V920 on HIV viral load, CD4 counts, and CD4/CD8 ratio.
- (4) **Objective:** Evaluate the safety and tolerability of two doses of V920 in HIV-infected adults and adolescents administered 56 days apart.
- (5) **Objective:** Evaluate the immunogenicity of two doses of V920 administered 56 days apart via ZEBOV-specific antibody responses induced by V920 at D28 post-dose 2 in HIV-infected adults and adolescents.

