#### 4.2.3.2 Safety Endpoints

1. Primary endpoints:
  - a. The occurrence of adverse events, in all participants, in all cohorts:
    - i. The occurrence of each solicited local and systemic AE, during a 14-day follow-up period following each vaccination, and fever, arthritis, arthralgia, rash and blisters/vesicular lesions during a 42-day follow-up period following vaccination.
    - ii. The occurrence of any hematological (hemoglobin level, WBC, lymphocyte, neutrophil, eosinophil and platelet count) and biochemical (ALT, AST and creatinine) laboratory abnormality at days 0, 3, 7, 14, and 28 after each vaccination.
    - iii. The occurrence of any unsolicited AE, during a 42-day follow-up period after each vaccination.
  - b. The occurrence of vaccine related SAE through to Day 365.
2. Secondary endpoints:
  - a. Detection of rVSV by PCR in blood, urine, and saliva in all subjects (D3, 7, 14, 28, 42 following each vaccination)
  - b. Detection of rVSV by PCR in through 42 days from skin vesicles, joint fluid, or skin biopsies if specimens are obtained
  - c. The occurrence of any SAE through to Day 365
  - d. Decrease in CD4 T cell-count (i.e.,  $CD4 < 200 \text{ mm}^3$ )
  - e. Increase in HIV viral load (i.e.,  $VL > 50 \text{ c/ml}$  over two consecutive measurements)

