#### 4.3.1.3 Reactions to V920

Detailed safety data collected in the Phase 2 and 3 studies to date have demonstrated V920 to be generally well-tolerated when administered to healthy, non-pregnant, adults. Injection site reactions following vaccination are generally mild to moderate and self-limited. Thereafter, there is a predictable period of early reactogenicity, including fever and a flu-like syndrome and resolves with 7 days. During this time, transient decreases in white blood cells and platelets

have also been observed but bleeding or increased risk of infection has not been reported. The early reactogenicity is likely to be a result of viremia with the vaccine virus which resolves within 2 weeks. Vaccine virus has been found in saliva, urine, and skin-vesicles in vaccines. Person-to-person transmission has not been documented, however transmission through shedding and close personal contact is accepted as a theoretical possibility. Joint pain (arthralgia) is part of the early flu-like syndrome in the first week after vaccination in up to 44% of vaccines. In a small proportion of subjects (<5%), joint swelling (arthritis) may develop in the 2nd to 3rd week after vaccination. The arthritis is thought to be virally-mediated, and while the majority of arthralgia and arthritis events resolved spontaneously, recurrent or persistent arthralgia and arthritis have also been reported. The safety profile reported from the Ebola-epidemic region has been similar to that observed outside the region.

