#### 5.1.2 Subject Inclusion Criteria

To be eligible for the study, each participant must satisfy ALL of the following criteria:

- 1) HIV-infected adult or adolescent male or non-pregnant, non-breastfeeding female, ages 13 to 70 (inclusive) at the time of screening;
- 2) On antiretroviral therapy with an undetectable viral load (< 40 c/ml);
- 3) CD4 T cell counts  $\geq 200$  cells/mm^3;
- 4) Written informed consent (subject or parent) and assent (adolescent), after reading the consent form and having adequate opportunity to discuss the study with an investigator or a qualified designee
- 5) Free of clinically significant health problems that could affect the safety of the participant, as determined by the Investigator by pertinent medical history and clinical examination prior to entry into the study;
- 6) Available, able, and willing to participate for all study visits and procedures;
- 7) Males and females who are willing to practice abstinence from sexual intercourse, or are willing to use effective methods of contraception, from at least 30 days prior to vaccination until 2 months after vaccination.
  - a. If the partner is NOT of childbearing potential, the couple will only be required to use condoms, without other adjunctive contraception.
  - b. For this study, a woman is considered of childbearing potential unless postmenopausal ( $\geq 1$  year without menses) or surgically sterilized (tubal ligation, bilateral oophorectomy, or hysterectomy)
  - c. Effective contraception is defined as a contraceptive method with failure rate of less than 1% per year when used consistently and correctly and when applicable, in accordance with the product label for example:
    - i. Male condoms PLUS:

- ii. Oral contraceptives, either combined or progestogen alone
- iii. injectable progestogen
- iv. implants of etenogestrel or levonorgestrel
- v. oestrogenic vaginal ring
- vi. percutaneous contraceptive patches
- vii. intrauterine device or intrauterine system

8) Be willing to minimize blood and body fluid exposure of others for 8 weeks after vaccination

- a. Avoiding the sharing of needles, razors, or toothbrushes
- b. Avoiding open-mouth kissing

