#### Vital signs & clinical laboratory measures

Mean values for each measure, including  $\pm$  one standard deviation, will be summarized for each treatment group. Shift tables may also be generated if a significant frequency of abnormalities is noted. Extreme values will be discussed individually.

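### The CD4-decrease safety endpoint is a fixed cut at 200 with no baseline term, so it is nearly blind in the higher CD4 cohorts and diluted near 200, and no baseline-adjusted analysis serves secondary objective 3.

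*Combined protocol and SAP*

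**What the plan says.** Secondary objective 3 (Section 3.2) is to "Evaluate the impact of V920 on HIV viral load, CD4 counts, and CD4/CD8 ratio". Section 4.2.3.2 serves it with two secondary safety endpoints. Endpoint 2.d is "Decrease in CD4 T cell-count", and its only definition is a count under 200. Endpoint 2.e, on the next line, is a viral load above 50 c/ml "over two consecutive measurements". No endpoint is given for the CD4/CD8 ratio.

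The inclusion criteria (Section 5.1.2) require "CD4 T cell counts" of at least 200, the same number as the endpoint threshold. The cohorts then run from 200–350 (Cohort 3) up to "Cohort 1: 50 adults with CD4" of 500 or more. Cohorts 4 and 5 take anyone at 200 or above.

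The flow charts (Section 6.0) schedule CD4/CD8 counts at screening, at Day 0 and at every later visit: 7 post-vaccination draws in Cohorts 1–4 and 13 in Cohort 5.

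Section 8.2.5.2 states that safety parameters will be compared between arms, but names tests only for local and systemic reactions. For laboratory measures it plans "Mean values for each measure, including" one standard deviation, by treatment group, with optional shift tables. Section 8.2.8 summarises safety by CD4 stratum and age. None of this text gives a change-from-baseline or baseline-adjusted analysis of CD4, CD4/CD8 or viral load.

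**The concern.** Whether a replicating vaccine disturbs HIV control is the safety question particular to this population. Objective 3 asks about impact on CD4, which means change. The endpoint records a state instead: below 200 or not.

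Because the cut equals the entry floor, the change needed to score depends on where the subject started. A move from 200 to 199 is an event, and a move from 700 to 280, a 60% loss, is not. A real fall in the higher cohorts could leave the event count at zero in both arms, while near 200 ordinary variation generates events in both arms and obscures a difference. If this count is the only pre-specified CD4 result, a null finding would say little.

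**Working it through.** **The nearest figure in the plan.** The documents give no power for the CD4 endpoint. Section 8.2.7 gives 80% power for a 12-point difference from a 1% control rate, 200 v 50. The normal approximation is power = Φ[(0.12 − 1.96·s₀)/s₁], where s₀ is the pooled and s₁ the unpooled standard error. With rates 0.01 and 0.13, the pooled rate is 0.106, s₀ = 0.0487 and s₁ = 0.0276, so power = Φ(0.89) = 0.81. The stated figure reproduces.

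**Step 1. Fall needed to score.** This is arithmetic with no assumption: the fall must exceed 1 − 200/baseline.

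| Baseline CD4 | 200 | 210 | 225 | 250 | 350 | 500 | 700 |
|---|---|---|---|---|---|---|---|
| Fall to exceed | 0 | 4.8% | 11% | 20% | 43% | 60% | 71% |

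**Step 2. Scoring without any vaccine effect.** Assume lognormal variation around a constant usual CD4 of B, with s = √ln(1 + CV²). One draw is below 200 with probability p = Φ[ln(200/B)/s], and at least one of k draws with probability 1 − (1 − p)^k. Example: for B = 225 and CV 20%, s = 0.198, p = Φ(−0.595) = 0.276, and 1 − 0.724⁷ = 0.90. The documents give no within-subject CV, so a range is shown. Averaging over B uniform on 200–350 (also an assumption):

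| Assumed CV | 10% | 15% | 20% | 25% |
|---|---|---|---|---|
| 7 draws (Cohorts 1–4) | 20% | 31% | 42% | 53% |
| 13 draws (Cohort 5 schedule) | 24% | 38% | 53% | 67% |

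The second row applies to Cohort 5 subjects whose CD4 lies in that band, not to all of Cohort 5. In Cohort 3 (40 V920, 10 placebo), the first row means about 8 to 21 V920 and 2 to 5 placebo subjects scored with no effect present.

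**Step 3. Scoring when there is a real fall.** Use the same model with B uniform on 500–900 (assumed), 7 draws, and every post-vaccination value multiplied by 0.7 or 0.5:

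| Assumed CV | 10% | 15% | 20% | 25% |
|---|---|---|---|---|
| Sustained 30% fall | 0.0% | 0.0% | 0.1% | 0.9% |
| Sustained 50% fall | 0.4% | 3.7% | 10% | 18% |

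The lowest band does respond: at CV 20%, a sustained 30% fall raises the 200–350 rate from 42% to 95%.

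**Step 4. What the dilution costs.** Cohort 3 is 50 of 250 subjects, so its noise alone adds 0.2 × 20% to 0.2 × 53%, or 4% to 11%, to the pooled rate. Cohorts 4 and 5 may add more, but their CD4 mix is not given. Using the plan's 12-point difference as a yardstick, power at 200 v 50 is 0.81 with a 1% placebo rate, 0.60 with 5% and 0.48 with 10%.

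**Step 5. What a continuous analysis could detect.** With 10% dropout (180 v 45), √(1/180 + 1/45) = 0.167. At 80% power and two-sided 0.05 the detectable fall is 1 − exp(−2.802 × SD × 0.167). For an assumed residual SD of log CD4 of 0.20 to 0.28, that is 8.9% to 12.3%. This is for one visit common to all cohorts.

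**The case against.** Much of the defence stands. Everyone screens at 200 or more, so a value below 200 is a crossing of the trial's own entry floor, and counting such crossings is a coherent question. The text does not say that any single value counts; that is the natural reading because 2.e has a confirmation rule and 2.d has none. Arm means would show a large CD4 shift if CD4 is treated as one of the laboratory measures, and Table 3 does list it among the laboratory tests. Lymphocyte abnormality is also a primary safety endpoint. This is a secondary endpoint in a Phase 2 trial, with no hypothesis attached.

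Four stronger readings are tempting, and the documents do not support them:

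- A reader might infer that the SAP has no comparative method. Section 8.2.5.2 does say safety parameters will be compared; for these markers the method is unspecified, which is different.
- A reader might infer that the endpoint mainly measures enrolment CD4 and number of draws. Randomisation is stratified by cohort and both arms follow the same draw schedule, so those factors balance between arms.
- Section 4.3.1.3 reports "transient decreases in white blood cells and platelets", and a reader might treat these as false CD4 events. The text does not mention CD4 cells, and a dip caused by V920 would be a vaccine effect, not noise. It is a reason to show early and later visits separately.
- A reader might extend the criticism to viral load. All subjects enter below 40 c/ml, so a 50 c/ml cut has a common baseline, and a confirmation rule exists. The one residue is that no confirmatory draw is scheduled after Day 365.

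Unadjusted means by arm remain a weak substitute for the missing analysis: they mix cohorts whose CD4 runs from 200 to above 500, which inflates the standard deviation, and they give no estimate or interval for the difference.

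**Conclusion.** The point holds. Endpoint 2.d cannot carry the CD4 part of objective 3, and CD4/CD8 has no endpoint. The insensitivity in subjects enrolled at 500 or more is arithmetic: only a measured fall of over 60% scores. The scoring rates also need the assumed CV and baseline spread. For a sustained 50% fall the blindness is strongest at 600 and above. At a baseline of exactly 500 and CV 20%, such a fall would score in 62% of subjects, through noise.

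The noise near 200 rests on the assumed CV but is material across the whole 10% to 25% range. Its consequence is lost power, not bias. Neither problem affects the primary endpoints, and every value needed for a better analysis is already collected.

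**What to change.** Make the main analysis for objective 3 a repeated-measures model of log CD4, and a second of log CD4/CD8, on treatment, visit, treatment-by-visit, baseline log value, cohort and site. Report V920/placebo ratios with 95% CIs by visit, with early visits (Days 3–14 after each dose) shown separately from later ones. State whether baseline is Day 0 or the mean of screening and Day 0. Post-dose-2 visits exist only in Cohort 5 (40 v 10), so label those estimates accordingly.

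Keep CD4 below 200 as a descriptive count by arm and CD4 cohort, once for any post-baseline value and once for two consecutive values. List a low value first seen at Day 365 as unconfirmed, so that it is not lost. Confirmation alone would not be enough: at a usual CD4 of 225 it cuts false scoring over 7 draws from 59–93% to 8–41%, but does nothing for subjects enrolled at 500 or more. At most, list a viral load above 50 c/ml first seen at Day 365 in the same way.

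The cost is one extra model form and SAP wording. No samples or visits are added. Objective 3 carries no hypothesis, so Section 8.0 allows the change to be documented in the supplemental SAP before database lock.

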#### 4.3 Benefit/Risk

Subjects in clinical trials generally cannot expect to receive direct benefit from treatment/vaccination during participation, as clinical trials are designed to provide information about the safety and effectiveness of an investigational medicine.

Potential risks may include those common to other vaccine products, and include local injection site reactions, as well as systemic reactions. The following sections discuss these potential risks in more detail and include brief descriptions for possible procedures to ameliorate risks and symptoms. All known risks and precautions described are explained in detail in the informed consent document. For live-attenuated vaccines such as V920 it is expected that the second dose of vaccine will have fewer safety concerns than the first dose of vaccine as the immune response from the first dose decreases viral replication.

### 4.3.1 Risks

#### 4.3.1.1 Local Reactions

Local reactions, with either V920 or placebo, may include pain, swelling, and/or redness at the injection site. Although highly unlikely, IM injections, independent of investigational product, can result in acute muscle damage, bruising, and/or injection site infection.

Vaccine will be administered by experienced and trained staff, using aseptic technique, in order to minimize or avoid these risks.

#### 4.3.1.2 Systemic Reactions

Systemic reactions include a predictable period of early reactogenicity which is common after receipt of other live-virus vaccines, and resolves spontaneously. On occasion, individuals may feel light-headed or faint after the act of injection or blood draw (vasovagal reaction).

Monitoring for these and other systemic symptoms commonly seen in investigational vaccine studies will be performed throughout the study, and addressed as required in order to maximize subject safety.

There is a theoretical risk of viral encephalitis or neurological impairment following vaccination with rVSV. As described previously, the vaccine vector has been specifically attenuated to eliminate neurovirulence, and the aforementioned NHP neurovirulence study supports the efficacy of this approach. Subjects will be closely monitored for vaccine neurological impact during the study.

Wild type VSV may also cause mild oral ulceration or stomatitis in humans. Volunteers will be closely monitored for such a manifestation and oral swabs will be performed to monitor for viral shedding in association with such a manifestation.

#### 4.3.1.3 Reactions to V920

Detailed safety data collected in the Phase 2 and 3 studies to date have demonstrated V920 to be generally well-tolerated when administered to healthy, non-pregnant, adults. Injection site reactions following vaccination are generally mild to moderate and self-limited. Thereafter, there is a predictable period of early reactogenicity, including fever and a flu-like syndrome and resolves with 7 days. During this time, transient decreases in white blood cells and platelets

have also been observed but bleeding or increased risk of infection has not been reported. The early reactogenicity is likely to be a result of viremia with the vaccine virus which resolves within 2 weeks. Vaccine virus has been found in saliva, urine, and skin-vesicles in vaccines. Person-to-person transmission has not been documented, however transmission through shedding and close personal contact is accepted as a theoretical possibility. Joint pain (arthralgia) is part of the early flu-like syndrome in the first week after vaccination in up to 44% of vaccines. In a small proportion of subjects (<5%), joint swelling (arthritis) may develop in the 2nd to 3rd week after vaccination. The arthritis is thought to be virally-mediated, and while the majority of arthralgia and arthritis events resolved spontaneously, recurrent or persistent arthralgia and arthritis have also been reported. The safety profile reported from the Ebola-epidemic region has been similar to that observed outside the region.

#### **4.3.1.4 Pregnancy**

Risks from the study vaccines to human fetuses are unknown at this time. As such, pregnant females will be excluded from participation. All female subjects of childbearing potential must be abstinent from intercourse with a male partner or utilize effective contraceptive precautions, as defined in the inclusion criteria (section 8.4), from 30 days prior to the date of vaccination through 2 months after the last vaccination. Non-childbearing potential is defined as either surgically sterilized or one year post-menopausal (defined as 12 consecutive months without menses).

Given the theoretical risk of transmission to a female partner of child bearing potential, male subjects will also be required to utilize effective contraception precautions for the same period of time.

#### **4.3.1.5 Lactation**

Risks from the study vaccines to nursing infants are unknown at this time. As such, breastfeeding females will be excluded from participation, and female subjects will be required to avoid breastfeeding during the study to minimize any potential risk.

#### **4.3.1.6 Venipuncture**

Some discomfort from the needle stick for the blood draw is possible, including swelling or bruising, and there is a very small risk of infection at the site of the needle stick. A few subjects may feel light-headed and may develop a rapid heartbeat during blood collection. These symptoms can be stopped by having the subject lie down and/or by stopping the procedure.

#### **4.3.1.7 Allergic Reaction**

As with any product, there is the potential risk of a serious, or even life-threatening, allergic reaction to one or more components of the investigational products to be used in this study. To mitigate this risk, potential subjects with a history of severe allergic reaction of any kind,

or significant allergic reaction to a known component of the experimental products, will be excluded from participation.

In the event of a severe allergic reaction, each study site is staffed with trained medical personnel and stocked with appropriate medical emergency equipment to provide acute care for conditions such as anaphylaxis. Further, a formal emergency medical response service at each study site, capable of treating and transferring any life-threatening injuries to a higher level of medical care, will be available.

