### 5.1.3 Subject Exclusion Criteria

Participants with any of the following criteria will be excluded:

1. History of prior infection with a filovirus or prior participation in a filovirus vaccine trial;
2. History of prior infection with VSV or receipt of a VSV-vectored vaccine;
3. Presence of any febrile illness or any known or suspected acute illness on the day of any first immunization (subject may be rescheduled);
4. Clinical manifestations of systemic diseases considered by the investigator to impact safety or immunogenicity
5. Receipt of systemic glucocorticoids (a dose  $\geq$  20 mg/day prednisone or equivalent) within one month, or any other cytotoxic or immunosuppressive drug within 12 months;
6. Receipt of any investigational drug within 12 months of vaccination;
7. Receipt of any live virus vaccine within 42 days prior to study entry or any other (non-live virus) vaccine within 14 days prior to study entry.
8. History of sensitivity to any component of study vaccines per investigator brochure or package insert;

**Any baseline laboratory screening tests which is outside of acceptable range as defined in the protocol (local site reference ranges): ALT, AST, creatinine, hemoglobin, platelet count, total white blood cell count, urine protein, urine occult blood, urine glucose AND considered clinically significant by the clinical investigator. The following five screening parameters have limits set:**

- a. absolute lymphocyte count  $\geq$ 1000 cells/mm^3
- b. hemoglobin not greater than 1.5 grams below the lower limit of the normal reference range at the local laboratory
- c. ALT, AST not greater than 2 to 2.5 times the upper limit at the local laboratory

- d. Platelet count  $\geq 125,000$  and  $\leq 550,000$
- 9. To exclude transient laboratory abnormalities, the investigator may repeat a specific test (E.g. hemoglobin) once during the screening period (I.e. a maximum of two tests), , and if the repeat test is normal, subject may be enrolled;
- 10. Have an active malignancy or history of metastatic or hematologic malignancy except non-melanoma skin cancers;
- 11. Suspected or known alcohol and/or illicit drug abuse within the past 5 years;
- 12. Moderate or severe illness and/or fever  $>101^{\circ}\text{F}$  ( $38.3^{\circ}\text{C}$ ) orally or  $> 100^{\circ}\text{F}$  ( $37.8^{\circ}\text{C}$ ) axillary within one week prior to vaccination;

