- 13. Pregnant or breastfeeding female, or female who intends to become pregnant during the study period;
- 14. Administration of immunoglobulins and/or any blood products within the 120 days preceding study entry or planned administration during the study period;
- 15. Any other significant finding that in the opinion of the investigator would increase the risk of the individual having an adverse outcome from participating in this study.

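### Section 4.3.1.7 promises to exclude anyone with a past severe allergic reaction from any cause, but the eligibility list in 5.1.3 makes only vaccine-component sensitivity a mandatory exclusion

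*Combined protocol and SAP*

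**What the plan says.** Section 4.3.1.7 describes the risk of a serious allergic reaction to a component of the investigational products. As mitigation it names two groups, joined by an or. The first is "potential subjects with a history of severe allergic reaction of any kind". The second, with the verb that governs both groups, reads "or significant allergic reaction to a known component of the experimental products, will be excluded from participation". The wording is categorical and leaves nothing to judgement.

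Section 5.1.3 is the operative exclusion list, and meeting any item excludes. Its only allergy item is exclusion 8: "History of sensitivity to any component of study vaccines per investigator brochure or package insert". Three other items depend on the investigator's assessment:

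- Inclusion 5 (5.1.2): "Free of clinically significant health problems that could affect the safety of the participant"
- Exclusion 4 (5.1.3): "Clinical manifestations of systemic diseases considered by the investigator to impact safety or immunogenicity"
- Exclusion 15 (5.1.3): "Any other significant finding that in the opinion of the investigator would increase the risk"

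Sections 7.1.1.2, 7.1.2 and 7.1.5.1 have the investigator or a designee judge eligibility against the inclusion and exclusion criteria. Section 7.1.5.1 points to Section 5.1 for those requirements.

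**The concern.** A safeguard that the risk section states as fixed becomes optional in the list that sites apply. Two investigators could see the same volunteer, say one with past anaphylaxis to a food, reach opposite decisions, and both comply with 5.1.3. The one who enrolled would have vaccinated a person whom 4.3.1.7 says will be kept out.

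There is also a consent question. Section 4.3 says that the risks and precautions it describes are explained in the consent document. That document was not available. If it repeats 4.3.1.7, volunteers are being told of an exclusion that the entry criteria do not impose.

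**Working it through.** The plan gives no figure to reproduce, so the check compares the text of Section 4.3.1 with the criteria.

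**Step 1: what 4.3.1.7 covers.** Its two limbs have different thresholds: a severe reaction from any cause, and a significant reaction to a component. The first cannot be read as component allergy only, because a severe component reaction already falls under the second limb and the first would then add nothing.

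**Step 2: match each stated exclusion to a criterion.**

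| Group that 4.3.1 says will be excluded | Where stated | Mandatory item in 5.1.3 |
|---|---|---|
| Pregnant: "pregnant females will be excluded from participation" | 4.3.1.4 | Exclusion 13 |
| Breastfeeding: "breastfeeding females will be excluded from participation" | 4.3.1.5 | Exclusion 13 |
| Significant reaction to a component | 4.3.1.7 | Exclusion 8 |
| Severe allergic reaction from any cause | 4.3.1.7 | None |

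Four groups are stated and three have a mandatory item: 4 − 3 = 1 unmatched. This counts text, not participants.

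**Step 3: can another item reach the unmatched group?** Inclusion 5 and exclusion 15 can, but only by judgement. Exclusion 4 is a weaker route, since a past, resolved reaction is not plainly a manifestation of systemic disease. None of the three requires exclusion.

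**Step 4: was the criterion deliberately dropped?** The Amendment History records no removal or narrowing of an allergy criterion. By contrast, when health care workers stopped being excluded (Amendment 7), the change was logged and then explained in 4.3.1.9. The log starts at version 2.2, so it cannot rule out an earlier choice.

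**Step 5: what a dose-2 exclusion would cost.** This bears on the scope of the fix, not on the defect. Primary hypothesis 2 (3.1) is tested in Cohort 5 at 28 days after the second dose. Section 8.2.7 gives 40 vaccine and 10 placebo recipients per cohort, and 5.8 says that discontinued subjects are not replaced. Losing one participant costs 1/40 = 2.5% of the vaccine arm or 1/10 = 10% of the placebo arm.

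**The case against.** The strongest reply is that little turns on this. The risk named in 4.3.1.7 is a reaction to a product component. Exclusion 8 makes that mandatory, in wording broader than 4.3.1.7 because it says sensitivity rather than significant allergic reaction. Investigators may still turn away anyone else they think at risk. The 30-minute observation (5.2), epinephrine and airway support (5.2.3) and emergency care (4.3.1.7) all remain. This stands, and it is why the point is minor.

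It can also be said that 4.3.1 is loosely worded narrative, not evidence of a lost criterion. Section 4.3.1.4 cites the inclusion criteria as section 8.4, although they are in 5.1.2, so 4.3.1 was not fully reconciled with the rest of the protocol. The silence of the log is weak evidence, and the parallel exclusions that were carried over amount to two sentences served by one criterion. This also stands: the documents do not show which text reflects the sponsor's intent. But the conflict does not depend on how it arose. Both sections are current and they disagree.

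Finally, the sponsor has been widening eligibility (age to 70, health care workers, laboratory limits), which argues for narrowing 4.3.1.7 instead of adding an exclusion. That is open to the sponsor, but it closes the inconsistency by giving up a stated safeguard and should be chosen knowingly.

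**Conclusion.** The concern holds as a minor internal inconsistency in a safety criterion. One of the four groups that 4.3.1 says will be excluded has no mandatory criterion and is left to investigator judgement. As written, such a person can be enrolled and vaccinated without breaching 5.1.3.

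The effect is on eligibility and participant safety only. How many participants it touches cannot be estimated. The conclusion rests on the protocol text; the investigator's brochure, consent form and any site screening forms were not available and might close the gap in practice.

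**What to change.** Add a history of severe allergic reaction from any cause to exclusion 8 in 5.1.3, checked at screening and again at Visit 1 before the first injection. State that an unrelated allergy predating a tolerated first dose is not, on its own, a reason to withhold dose 2 in Cohort 5. The Cohort 5 flow chart appears to show a further eligibility check at the dose-2 visit (its columns are shifted in the extracted text), so the exception should be written there too.

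The text change is short, but it needs the amendment approvals described at the end of the Amendment History. Medical history is already taken before the first injection (7.1.1.4), so no new visit or procedure is needed. That section does not name allergy, however, and a specific screening question may be required. Some extra screen failures will follow; the documents do not allow their number to be estimated.

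If the sponsor does not intend the exclusion, narrow 4.3.1.7 to component sensitivity and confirm that the consent text agrees. That changes nobody's eligibility but withdraws a stated mitigation.
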